EFFECT OF TOPICAL INTRA-AURICULAR LIDOCAINE ON TINNITUS: A RANDOMIZED DOUBLE-BLIND PLACEBO-CONTROLLED STUDY. NCT05711641

AUGUST 04, 2022

STUDY PROTOCOL AND STATISTICAL ANALYSIS PLAN:

Tinnitus is a prevalent symptom, which can drastically impact the quality of life of the individual and for which there is still no proven effective treatment. Lidocaine has been widely investigated with high rates of tinnitus suppression, but its systemic use has not been shown to be viable due to the fleeting response and the risk of potentially serious side effects. The clinical observation of the improvement of chronic tinnitus in some individuals after the use of otological drops indicated for the treatment of otitis externa aroused our interest in the action of topical intraauricular lidocaine in reducing the intensity of tinnitus, motivating the realization of this study.

The objective of this study is to evaluate the action of 10% topical intraauricular lidocaine on the perception of tinnitus intensity compared to placebo.

This project was designed as a randomized, crossover, placebo-controlled, double-blind, randomized clinical trial. It was approved by the Research Ethics Committee (REC) of the host institution under opinions number 4.188.11 and 5.562.868, and was registered at ClinicalTrial.gov under identification number NCT05711641. The participants were properly informed and signed a informed consent form.

The selected subjects were patients of an otolaryngology center who sought care for tinnitus complaints between April 7, 2021, to April 6, 2022. Of them, 113 patients met the inclusion criteria, and none of the exclusion criteria, and were invited to participate in the study through WhatsApp contact. Thirty-three patients responded and attended the initial appointment, one was excluded for having only pulsatile tinnitus on the day of the appointment. Thirty two patients were enrolled and 28 completed both assessments.

The inclusion criteria were age over 18 years, continuous tinnitus for at least six months, and a visual analog scale (VAS) tinnitus intensity score of at least three points on the days the substances were administered. The exclusion criteria were otologic infection, tympanic membrane perforation, anatomic external ear changes, pulsatile tinnitus, objective tinnitus, known allergy to lidocaine or other topical anesthetics, pregnancy, cardiac arrhythmia, epilepsy, previous history of seizure, or use of anticonvulsants.

The website www.randomization.com was used to define the order of substance administration, defining whether the patient would start the study as a case or a control. The subjects were randomized by the "Heads or Tails" method in cases of bilateral and symmetrical tinnitus, with one Real coin (official currency of the country) being tossed by the patient himself. "Heads" was previously defined as the right ear, and "tails" as the left ear. In the case of bilateral and asymmetrical tinnitus, the study ear was the ear where the tinnitus was perceived with greater intensity.

The subjects were evaluated regarding the action of intra-auricular topical lidocaine on tinnitus intensity compared to a placebo. The study ear was defined in the first evaluation, the order of substance administration was randomized, and the patients had their medical history researched and underwent physical examination with somatosensory tinnitus analysis and audiological evaluation.

Tinnitus intensity in each ear was measured by the VAS, which ranged from 0–10 points, immediately before each administration and immediately after the substances were removed. The VAS was also used to evaluate somatic maneuvers to determine tinnitus modulation, considered positive in the case of a VAS score variation in at least one of the maneuvers.

An audiological evaluation was carried out in an acoustically treated booth, with TDH 39 and HD 200 headphones, using the MADSEN Itera II audiometer. The tonal threshold between 250–16 kHz was researched by an ascending and descending technique. A tonal threshold up to 8 kHz was classified according to the criteria by Lloyd and Kaplan. The audiometric threshold of high frequencies (9–6 kHz) was measured to determine the tinnitus pitch in these frequency ranges.

The psychoacoustic measures used for analysis in this study were the tinnitus loudness and the minimum masking level (MML), measured in decibel sensation level (dBSL) and performed before and after the application of each of the substances. The pitch was assessed by pure tone sound stimuli or narrow band (NB) noise, being measured in Hz.

Tinnitus loudness was analyzed by presenting the sound most similar to the patient's tinnitus, determined by the pitch, in the ipsilateral ear in cases of unilateral tinnitus or the ear with better hearing in cases of bilateral tinnitus, increasing the intensity by 1 dB until finding the volume closest to the patient's tinnitus.

The MML was assessed by an NB sound presented to the ipsilateral ear. Starting from the patient's threshold detected for this type of sound, the volume was increased by 1 dB every four seconds until the presented sound masked the tinnitus.

The substances used were 10% lidocaine (active substance) or distilled water (placebo). They were produced in the same compounding pharmacy, being replaced by new ones every 90 days and being stored in identical bottles identified as: "Substance 1" and "Substance 2."

The patient was positioned in a lateral decubitus position, with the tested ear facing up, and 20 drops of the randomized substance were administered and remained in the external acoustic meatus (EAM) for five minutes at each treatment session. For medication removal, the patient was instructed to sit with their head tilted to the side of the study ear, the substance was removed by gravity, and the ear was dried with gauze.

Each ear was its own control and crossover administration was two weeks apart.

Data analysis:

The mean VAS, tinnitus loudness, and MML were compared between lidocaine and the placebo before and after the administration of each substance to evaluate the effect of lidocaine on tinnitus.

To investigate whether any characteristics of the sample correlated with tinnitus variation after the administration of the substances, we compared the VAS, tinnitus loudness, and MML variations related to the variables sex, bruxism/ temporomandibular disorder (TMD), cervical changes, somatosensory tinnitus, modulation, and hearing loss.

Statistical analysis:

Qualitative characteristics of patients and tinnitus were described using absolute and relative frequencies, and quantitative characteristics were described using summary measures (mean, standard deviation, median, minimum, and maximum value). VAS, tinnitus loudness, MML, and variations for each administration were described using summary measures, and the variations between substances were compared using Generalized Estimating Equations (GEE) with marginal normal distribution and identity link function, assuming an interchangeable correlation matrix between substances.

The analyses were performed using the IBM-SPSS for Windows version 22.0 software and tabulated using the Microsoft Excel 2010 software. Statistical significance was set at 5%.

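### Does a VAS threshold that applies on both administration days, with no named analysis set, put the crossover comparison at risk?

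*Combined protocol and SAP*

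**What the plan says.** The eligibility paragraph lists, among the inclusion criteria, "a visual analog scale (VAS) tinnitus intensity score of at least three points on the days the substances were administered". The plural covers both visits, since the administration paragraph states: "Each ear was its own control and crossover administration was two weeks apart".

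Order of events:

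- On the first evaluation: "The study ear was defined in the first evaluation, the order of substance administration was randomized".
- VAS is recorded "immediately before each administration and immediately after the substances were removed", so the first-period change is complete two weeks before the second-day score exists.

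On participant flow, the selection paragraph reports: "Thirty two patients were enrolled and 28 completed both assessments". It gives no reasons for the four who did not.

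On the model, the Statistical analysis section says that "the variations between substances were compared using Generalized Estimating Equations (GEE) with marginal normal distribution and identity link function", with an exchangeable working correlation between substances. It names no analysis set and has no rule for a missing period.

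**The concern.** An inclusion criterion is normally settled before randomisation. Here half of it is settled afterwards, by a score that the first substance could have altered. Two readings are open. Under the literal one, a patient below 3 on the second day fails inclusion and can be dropped together with a valid first-period result. Under the other, the score governs only that day's administration and the first period stays in. The GEE runs under either, so two analysts could follow the plan and analyse different patients.

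If lidocaine still lowered tinnitus two weeks later, responders who had it first would fall below 3 more often than patients who had placebo first. The literal reading would then remove responders selectively, and a completers-only estimate would shrink toward zero. In a trial of 32, a real effect could be missed.

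**Working it through.** **What the documents give.** Enrolled: 33 − 1 = 32. Not completing both assessments: 32 − 28 = 4, or 4/32 = 12.5%. If all 32 received the first substance (not stated), keeping every recorded period gives 32 + 28 = 60 patient-periods. Completers alone give 2 × 28 = 56. The two readings therefore differ by at most four first-period records, and 56/60 = 93% of the data are common to both. There is no sample-size calculation, baseline VAS or effect size to reproduce.

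**How often the second-day rule would bite without carry-over.** This needs assumptions. For a baseline VAS mean of 5 to 7, SD 1.5 to 2.5 and between-day correlation 0.5 to 0.7, the chance of a score below 3 on day 2 after an eligible day 1 runs from about 0.1% to 11%, or about 0 to 4 of 32 patients. The input sets of the simulation below give 3% to 8%, or 1.0 to 2.5 of 32.

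**What removal would do to the estimate.** All simulation inputs are assumed: VAS rounded to 0–10, within-patient visit SD 1, post-dose noise SD 0.5, placebo change −0.5, no period effect, 16 patients per order. In the base case baseline has mean 5 and SD 1.5, and 30% respond to lidocaine by −3. Persistence at two weeks is defined in two ways. S: that share of responders keeps the full effect. D: every responder keeps that share of the effect. Removal among placebo-first patients stays near 5%.

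| Persistence | Removed, lidocaine first (S / D) | Completer estimate pulled toward zero (S / D) | Power: all recorded periods vs completers (S / D) |
|---|---|---|---|
| 0% | 5% | none | 89% vs 88% |
| 25% | 9.1% / 7.2% | 3.8% / 1.2% | – |
| 50% | 13.0% / 10.8% | 9.3% / 5.9% | 89% vs 80% / 82% |
| 100% | 21% | 21% | 89% vs 70% |

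Across five input sets the pull toward zero is 3.8–10.5% (S) or 2.3–7.6% (D) at 50% persistence, and 8.5–24.5% at 100%. In standard errors for 28 pairs, that is 0.08–0.30 and 0.29–0.74. With no persistence the completer estimate is 0.8–2.5% further from zero than the full-data estimate.

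These sets use baseline means of 4.5 to 6. With mean 7, SD 1.5 and 30% responders, the pull at 50% persistence is 3.6% (S) or 1.3% (D) for an effect of −3, and 1.4% or 0.7% for −2. At 100% it is 7% or 3%. The documents do not say which range fits.

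**What the GEE does if first periods are kept.** Across the scenarios of the five input sets it runs from 2.1% further from zero to 0.5% closer than the full-data estimate, so within about 2%.

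**Check against observed attrition.** At 100% persistence the base case implies about 16 × (0.21 + 0.05) = 4.2 removals for low VAS. The trial lost four patients for all reasons. The extreme case would therefore use up the whole attrition, if removed patients are among those four. If they were dosed and counted among the 28, this check does not apply.

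**The case for a change.** The strongest case for a change is that the ambiguity is certain even though the bias is conditional. The criterion does reach past randomisation, the plan has no analysis set, none of this comes from redaction, and 12.5% of a small trial has no stated handling. A few sentences would settle it at little cost. Counts of non-completers by order could not settle it later: with 16 per order (assumed), even a 4–0 split has a two-sided exact p of 2 × C(16,4)/C(32,4) = 2 × 1,820/35,960 = 0.10.

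The description of the gap stands. The step from gap to harm does not. Three things must hold together: the literal reading was applied, some patients scored below 3 on the second day, and an effect of a five-minute topical application lasted two weeks. None is shown. The only remark on duration concerns systemic lidocaine, of which the protocol says "its systemic use has not been shown to be viable due to the fleeting response". That does not rule out persistence after topical use, but it lends it no support. If persistence did exist, carry-over itself would be the larger problem, and an analysis-set statement would not cure it. The selection also works in one direction in this model: it can hide an effect but does not create one.

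A prescriptive rewrite would bring its own difficulties. VAS is recorded in each ear while the criterion names none, and no outcome is designated primary. A sentence setting aside a stated inclusion criterion would need further choices that the documents do not settle.

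**Conclusion.** The criterion is loosely placed and the analysis set is unstated, but the plan needs no change on this account. An analyst running the specified GEE on the recorded data keeps single-period patients without departing from the text. Under the assumed inputs that analysis stays within about 2% of the full-data estimate, whatever the persistence. Even the literal reading costs about one percentage point of power in the base case when no effect persists. The larger figures (21–24% attenuation, 70% power) require every responder to keep the full effect for two weeks and are upper bounds, not expectations.

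This conclusion rests on two points: nothing in the documents shows a removal for low second-day VAS, and nothing in them supports a two-week effect. Evidence of both would reopen the question. How the criterion was applied, and why four patients did not finish, belongs in the participant flow of the trial report.

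### No period term is stated for the crossover GEE; a visit difference in response would widen the lidocaine-placebo standard error and, with unequal orders, shift the estimate

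*Combined protocol and SAP*

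**What the plan says.** The trial is a two-visit crossover. A randomisation website "was used to define the order of substance administration, defining whether the patient would start the study as a case or a control". On timing, the document says: "Each ear was its own control and crossover administration was two weeks apart". VAS was recorded "immediately before each administration and immediately after the substances were removed", and loudness and MML were likewise "performed before and after the application of each of the substances". The quantity analysed is the change at each administration.

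For the main comparison, the Statistical analysis section states that "the variations between substances were compared using Generalized Estimating Equations (GEE) with marginal normal distribution and identity link function". It describes how the two visits of a patient are linked as "assuming an interchangeable correlation matrix between substances". This fixes the distribution, link and working correlation. It does not list the model's predictors or say which variance estimator was used. Period, visit and sequence appear nowhere as model terms, and the number of patients in each order is not given. The Data analysis section separately compares "variations related to the variables sex, bruxism/ temporomandibular disorder (TMD), cervical changes, somatosensory tinnitus, modulation, and hearing loss"; visit and order are not among these six.

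The document describes completed work: "The analyses were performed using the IBM-SPSS for Windows version 22.0 software". It reports 32 patients enrolled and 28 with both assessments.

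**The concern.** Each patient is treated once at visit 1 and once at visit 2, so any systematic difference between visits is part of the design. Using the within-visit change removes a difference in tinnitus level between visits. It does not remove a difference in the change itself. Two sources are plausible: a larger non-specific response at the first visit, and practice on the 1-dB loudness-matching and masking tasks. The documents give no size for either, and it may be zero.

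If a visit difference exists and the model holds only substance, two things follow. The difference is counted as within-patient noise, so the standard error is larger than it need be. If more patients received one order than the other, a fraction of it also enters the lidocaine-placebo estimate. With 28 completers there is little precision to spare. A reader can check none of this, because the predictors, the variance estimator and the order counts are all missing.

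**Working it through.** The plan gives no sample size calculation, SD or effect size, so there is no stated figure to reproduce.

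**Inputs.** From the document: 28 patients with both assessments, randomised order, 5% significance level. Assumed: complete pairs only; two-sided tests; visit effect π of 0 to 1 VAS point; SD of within-patient differences 1.5 to 2.5; true lidocaine-placebo difference τ = 1 point in size.

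**Set-up.** Let d be a patient's lidocaine change minus placebo change, with within-order standard deviation SD, and let π be the visit-2 minus visit-1 difference in change. The mean of d is τ − π for the n1 patients given lidocaine first and τ + π for the n2 given placebo first.

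- Without period: the estimate is the mean of all d, shifted by −π(n1 − n2)/28. Its reported variance is about [SD² + 4π²·n1·n2/(28·27)]/28.
- With period: the estimate is the average of the two order means, with no shift. Its variance is SD²(1/n1 + 1/n2)/4.

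**Step 1: ratio of standard errors, without versus with period.** At 14/14 and π/SD = 0.5: 4 × 0.25 × 196/756 = 0.259, and √1.259 = 1.122.

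| Split | π/SD = 0 | 0.25 | 0.5 | 0.67 |
|---|---|---|---|---|
| 14/14 | 1.000 | 1.032 | 1.122 | 1.209 |
| 16/12 | 0.990 | 1.021 | 1.108 | 1.192 |

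The ratios depend only on π/SD, so they hold for loudness and MML too.

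**Step 2: power at 14/14 with τ = 1 (simulation).** The last two columns apply if the test used an uncorrected robust standard error.

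| π, SD | t-based, no period | t-based, with period | Robust, no period | Type I error of that robust test |
|---|---|---|---|---|
| 0, 2 | 72% | 72% | 76% | 6.5% |
| 0.25, 2 | 72% | 72% | not tabulated | not tabulated |
| 0.5, 2 | 70% | 72% | not tabulated | not tabulated |
| 0.5, 2.5 | 52% | 53% | 57% | 6.0% |
| 1, 2 | 64% | 72% | 69% | 3.9% |
| 1, 1.5 | 85% | 92–93% | 88% | 2.7% |

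**Step 3: type I error.** For the t-based test without period, in the four scenarios that have robust figures above (same order), it is 5.1%, 4.6%, 2.9% and 1.9% at 14/14, and 5.1%, 4.8%, 4.0% and 3.4% at 16/12. With period (π = 1, SD 2; 14/14 to 16/12), it is 7.0–7.1% with an uncorrected robust standard error, 5.3% with the Mancl-DeRouen correction, and 5.0–5.1% with a pooled t on 26 df.

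**Step 4: unequal orders, π = 1, SD 2.** At 15/13 the shift is 2/28 = 0.07 VAS point, or 0.17 of the reported standard error. At 16/12 it is 4/28 = 0.14, or 0.34 of the reported standard error. At 16/12, t-based power without period is about 50% or 76%, depending on which order is larger, against 71% with period.

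**Step 5: how likely is an uneven split?** Under simple 1:1 randomisation, 16/12 or worse among 28 has probability 0.57. If the 32 were allocated 16/16 and four were lost at random, 16/12 requires all four from one order: 2 × 1,820/35,960 = 0.10. The allocation method does not tell us which applies.

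**The case against.** The strongest reply is that the omission is inferred. The section lists no predictors at all, so what is established is incomplete reporting; a period term may have been fitted. The list of six variables is weak evidence either way, because it covers characteristics of the sample, and visit and order are design factors. Both points stand.

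Second, the harm needs a visit effect that the documents do not report, and analysing change scores already removes the more obvious kind. At 14/14 and SD 2, a visit effect of 0.5 point costs about 2 percentage points of t-based power; the 8-point loss needs a visit effect as large as the assumed treatment effect. This also stands.

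Third, the substance-only analysis is valid on average. Over simple randomisation the shift averages to zero, and the t-based type I error is 5.0% at every π tried. The standard error is too large, and the estimate shifted, only given the split that actually occurred. That is correct, and it makes this a question of efficiency and of accuracy for the realised split, not of systematic bias.

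Fourth, the 6.0% to 6.5% type I error of an uncorrected robust standard error is a small-sample variance problem that exists without any visit effect. True, but the two cannot be handled separately here, because adding period while keeping that standard error raises the error rate to about 7%.

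None of this removes the need to state the model, and period adjustment costs almost nothing.

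**Conclusion.** The concern holds and should be fixed, with medium confidence because the fitted model is not fully described. No period term is stated. Given a visit difference in the change, a substance-only GEE reports a standard error 3% to 21% too large at 14/14 (visit effect 0.25 to 0.67 SD). It also shifts the estimate by (n1 − n2)/(n1 + n2) of the visit effect when the orders are unequal. With no visit effect there is no loss. Whether the test is conservative depends on the visit effect, the split and the variance estimator: a t-based test is conservative near balance when a visit effect exists, while an uncorrected robust test exceeds 5% when that effect is small or absent.

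All sizes rest on the assumed visit effects and SDs and on 28 complete pairs; the plan does not say whether the four patients without both assessments enter the GEE. Nothing here shows that a reported result is wrong. Carryover is a separate matter and is not addressed.

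**What to change.** State the GEE predictors, the variance estimator and the number of patients per order. If period was already in the model, saying so and naming the variance estimator may be enough, provided that estimator is suited to 28 patients.

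Otherwise, add a period-adjusted analysis for VAS, loudness and MML, labelled as added after the original plan. It needs two parts together: visit (1 or 2) as a fixed factor beside substance, and a small-sample variance or t reference. The term should not be added with an uncorrected robust standard error.

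The simplest version needs no GEE option. For each patient take the visit-1 change minus the visit-2 change, and compare the two orders with a two-sample t-test on 26 df. The order means are τ − π and −τ − π, so half their difference (lidocaine first minus placebo first) is the period-adjusted lidocaine-minus-placebo effect. A linear mixed model with substance and period gives the same estimate. Report it with its 95% confidence interval.

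The cost is one extra model or t-test per outcome, on data already collected, and about one degree of freedom. With no visit effect the standard error is unchanged at 14/14 and about 1% larger at 16/12. The result is post hoc and must be presented as such.

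### The GEE on pre-to-post variations names no baseline covariate and so fixes the slope on the pre-administration value at 1, which may cost precision but does not bias the comparison

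*Combined protocol and SAP*

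**What the plan says.** The trial is a two-period crossover: "This project was designed as a randomized, crossover, placebo-controlled, double-blind, randomized clinical trial". VAS was recorded "immediately before each administration and immediately after the substances were removed", and loudness and MML were "performed before and after the application of each of the substances", so each outcome has its own baseline in each period.

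Under Statistical analysis, "the variations between substances were compared using Generalized Estimating Equations (GEE) with marginal normal distribution and identity link function", with an exchangeable working correlation. That section names no covariate. Under Data analysis, "The mean VAS, tinnitus loudness, and MML were compared between lidocaine and the placebo before and after the administration of each substance". This would display a difference in pre-administration means but does not adjust for one. The patient characteristics listed there for a separate exploratory comparison do not include the pre-administration value.

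On numbers: "Thirty two patients were enrolled and 28 completed both assessments".

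**The concern.** Analysing post minus pre is the same as modelling post with the pre-value's coefficient held at 1. If the true within-patient slope is below 1, subtracting the whole pre-value adds noise that an estimated slope would remove. The baselines have already been collected, and with only 28 complete pairs precision is scarce. At stake are the width of the confidence interval and the chance of detecting a real effect. The validity of the comparison is not in question.

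**Working it through.** The documents give no power, effect size or SD, so there is no planned figure to reproduce.

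**Inputs.** n = 28 complete pairs (participants paragraph). Significance level 5% (Statistical analysis), taken as two-sided because sidedness is not stated. For each patient let Dpre and Dpost be the lidocaine-minus-placebo differences in pre and post values. Let r be their correlation and k = SD(Dpost)/SD(Dpre). Both r and k are assumptions, so a range is shown.

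**Step 1: is the slope really 1?** On 28 simulated pairs, an exchangeable GEE on the variation and a GEE on post with pre as an offset gave the same estimate, −0.7296. This also equalled the mean within-pair difference in variation. The slope is fixed at 1.

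**Step 2: bias.** Trials of 28 pairs were simulated in 16 settings, 6,000 each. The settings were r from 0.3 to 0.9, true effect 0 or −0.8, with and without the VAS entry rule and the 0–10 bounds. Assumed SDs were 1.5 between and 1.2 within patients. The mean change-score estimate was within 0.011 of the truth throughout, and rejection under no effect was 4.4% to 5.5%. There is no bias to correct.

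**Step 3: variance.** In units of Var(Dpre):

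- change score: 1 + k² − 2rk
- adjusted: k²(1 − r²) × (n − 3)/(n − 4), where the last factor, 25/24 at n = 28, is the cost of estimating the slope with sequence in both models

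Ratio, adjusted to change score = (25/24) × k²(1 − r²)/(1 + k² − 2rk).

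Example, k = 1 and r = 0.5: (25/24) × 0.75/1 = 0.78.

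For power, take an effect that the change score detects with 80% power. On 26 df this is a noncentrality of 2.91. The adjusted analysis has noncentrality 2.91/√ratio on 25 df. At k = 1 and r = 0.5 that is 2.91/√0.781 = 3.29, or 89% power. The third column is 1/ratio − 1.

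| k, r | Variance ratio | Worth in patients | Adjusted power |
|---|---|---|---|
| 1, 0.3 | 0.68 | +48% | 92% |
| 1, 0.5 | 0.78 | +28% | 89% |
| 1, 0.75 | 0.91 | +10% | 83% |
| 1, 0.9 | 0.99 | +1% | 80% |
| 1, 0.95 | 1.02 | −2% | 79% |
| 1.2, 0.5 | 0.91 | +10% | 84% |
| 1.2, 0.75 | 1.03 | −2% | 79% |
| 1.2, 0.85 | 1.04 | −4% | 78% |
| 0.8, 0.5 | 0.60 | +68% | 95% |
| 0.8, 0.75 | 0.66 | +51% | 93% |
| 0.8, 0.9 | 0.63 | +58% | 94% |

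With k = 1 the ratio reduces to (25/24)(1 + r)/2, which equals 1 at r = 48/25 − 1 = 0.92.

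**Step 4: the bound.** (1 + k² − 2rk) − k²(1 − r²) = (1 − rk)², which is never negative. Apart from the factor 25/24, adjustment cannot do worse. The largest possible loss is 4.2% in variance, reached when the true slope rk is 1; power then falls from 80% to about 78%.

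**Step 5: simulation of the formula.** With 14 patients per sequence and 40,000 runs per cell, k = 1 gave ratios of 0.680, 0.783, 0.914, 0.991 and 1.017 at r = 0.3, 0.5, 0.75, 0.9 and 0.95. For k = 1.2 they were 0.904, 1.026 and 1.040 at r = 0.5, 0.75 and 0.85. Type I error with a t reference was close to 5% for both analyses.

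**The case against.** A prespecified change score in a randomised crossover is standard, interpretable and unbiased, so preferring an adjusted analysis can look like taste. The gain is also unknown, and the design suggests it may be small. The substance "remained in the external acoustic meatus (EAM) for five minutes at each treatment session", so the two readings are minutes apart. Session-to-session fluctuation is common to both and raises r. With k = 1 and r of 0.75 or more, power moves by about three points at most. Enrolment and completion are already reported and the analyses are described in the past tense, so a late change cannot recover confirmatory power.

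Most of this stands, and it is why the point concerns efficiency only. It does not remove the point, for two reasons. First, a high r alone does not make the change score efficient; the product rk must be near 1. VAS entry required a "tinnitus intensity score of at least three points on the days the substances were administered", while the post value may fall to 0, so equal SDs are not assured. Three outcomes on different scales also need not share one slope. Second, the downside is capped at 4.2% of variance, while the upside is several times larger over much of the range.

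It is also fair that the comparator in the working includes sequence, which the documented GEE does not name, and that a difference regression drops any patient with only one session. Four of the 32 enrolled (32 − 28) did not complete both assessments.

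**Conclusion.** The concern holds as a possible loss of precision. No baseline covariate is named, the slope is fixed at 1, and the planned comparison is nonetheless valid. Over the values tabulated, the adjusted variance runs from 0.60 to 1.04 times that of the change score. Where the trial lies in that range cannot be told from the documents.

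This rests on assumed r and k, approximate normality, 28 complete pairs and a two-sided 5% test. The statement that there is no bias also assumes that the first substance does not affect the second pre-administration value, and that non-completion causes no selection. Those are separate matters that the missing covariate does not create. The point merits a change to the plan or an added analysis, but it gives no reason to set aside the planned result.

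**What to change.** For each of VAS, loudness and MML, regress the within-patient post difference (lidocaine minus placebo) on the pre difference and sequence by least squares, with a t reference on 25 df for 28 pairs.

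If GEE is kept, include substance, period and the pre-value split into the patient's mean and the period-specific deviation. A single pooled slope would mix between- and within-patient information. On complete pairs this gives the same estimate as the difference regression. State how patients with one session are handled, since GEE can use them and the difference regression cannot.

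Also state bias-corrected standard errors with a t reference. In simulation at n = 28 (5,000 runs each at r = 0.5 and 0.75), an uncorrected sandwich with a normal reference rejected 6.2–6.3% under no effect with substance only, and 7.4–7.5% with period, mean and deviation added. Kauermann–Carroll standard errors with a t reference brought the latter to 4.7–5.2%. The documents state neither the type of standard error nor the reference distribution, so the uncorrected case is an assumption.

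Make this the main model only if it is fixed before unblinding. Otherwise keep the planned comparison of variations as the main result and report this as a labelled post hoc sensitivity analysis.

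The cost is two or three sentences of SAP text and no new data. It uses one degree of freedom in the difference regression, or two in the GEE, with the capped variance penalty shown above.
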